The following power calculations assume 80% power and a 2-tailed type 1 error of 0.05. Data from the pilot study in pediatrics showed that of all children in the study, only 49% reported a prior diabetic eye exam, and this increased to 95% with the implementation of POC AI screening.⁴ National data show that 42% of youth with T2D and 66% of youth with T1D had a diabetic eye exam by 6 years after initial diabetes diagnosis,¹ and our preliminary data showed that of youth who met ADA criteria for DR screening, 66% had a prior diabetic eye exam (46% non-white, 85% white youth). We assume that adding the educational intervention will raise the ECP rate to 60%. Randomization and study visit occur at the same time so there is little risk of attrition, and thus the study sample size will not be expanded to account for attrition. To show difference in proportion of who gets screened we assess a 20% difference to be clinically relevant between the two

strategies. Committing to demonstrating this difference results in a sample size of 164 (n=82 ECP, n=82 AI).

E2. Interim Monitoring and Early Stopping

One interim efficiency analysis for efficacy is planned. Using the alpha spending function with O'Brien and Fleming stopping rules, we will stop the trial if we show efficacy at the $p < 0.0054$ level. To adjust for the interim look, if the trial continues to the planned full sample size, the threshold for significance will be $p < 0.0492$.

Although consideration may be given to stop the study early because of an apparent beneficial treatment effect, early termination for efficacy will be considered with caution because of the degree of uncertainty with regard to the long-term benefit of treatment even if a short-term benefit seems apparent prior to the completion of the study. This will be determined by the independent DSMB committee.

E3. Analysis Plan

Primary outcome variable.

The primary outcome is the *proportion* of participants who get screened between AI and ECP. The comparison will be assessed using a Pearson's chi-square test (primary outcome) and logistic regression (adjusting for covariates).

Secondary outcome variables.

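### E2 gives neither the look time nor the O'Brien-Fleming version, and at a halfway look its thresholds of 0.0054 and 0.0492 have a joint two-sided error of about 0.0513, not 0.05

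*Combined protocol and SAP*

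**What the plan says.** - **Error rate (E1).** The sample size calculations "assume 80% power and a 2-tailed type 1 error of 0.05". They lead to 82 participants per arm for 60% versus 80% screened.
- **Number of looks (E2).** "One interim efficiency analysis for efficacy is planned".
- **Rule (E2).** "Using the alpha spending function with O'Brien and Fleming stopping rules".
- **Thresholds (E2).** At the interim, "we will stop the trial if we show efficacy at the $p < 0.0054$ level". If the trial runs to full size, "the threshold for significance will be $p < 0.0492".
- **Discretion (E2).** The next paragraph says that "early termination for efficacy will be considered with caution" and leaves the decision to the independent DSMB.
- **Not stated anywhere.** The documents give no information fraction, no number randomized and no number with known outcomes at the look. They do not say whether the classical O'Brien-Fleming boundary or a particular spending function is used.

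**The concern.** A spending function allots type 1 error as a function of information time. Without the look time and the form of the function, the two thresholds cannot be derived from the rule that E2 names, and their exact joint error cannot be confirmed. The numbers also look inconsistent with that rule: a final level of 0.0492 gives up only 0.0008 of the 0.05, although 0.0054 is available at the interim. These thresholds decide the primary claim. If they do not fit together, a result between the correct final level and 0.0492 would be declared significant when it should not be.

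**Working it through.** **Inputs.** The overall two-sided error of 0.05, 82 per arm and 60% versus 80% come from E1. The interim level 0.0054 and final level 0.0492 come from E2. The Pearson chi-square test comes from E3. The information fraction t is not in the documents; t = 0.5 is an assumption, and other values are shown.

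**Step 1: critical values.** Two-sided p of 0.0054 is z1 = 2.782, and 0.0492 is z2 = 1.967. Then (1.967/2.782)² = 0.500. The classical O'Brien-Fleming boundary has z1 = c/√t and z2 = c, so the ratio has the shape of a look at t = 0.5. The constant that holds 0.05 there is c = 1.977, not 1.967.

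**Step 2: joint error of the stated pair.** With Z1 and Z2 standard bivariate normal and correlation √t,

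error = 1 − P(|Z1| < 2.782, |Z2| < 1.967).

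| Look at t | Joint error, 0.0054/0.0492 | Final level that holds 0.05 with 0.0054 |
|---|---|---|
| 0.40 | 0.0520 | 0.0472 |
| 0.50 | 0.0513 | 0.0479 |
| 0.60 | 0.0506 | 0.0485 |
| 0.70 | 0.0500 | 0.0492 |

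A simulation of 20 million draws at t = 0.5 also gives 0.0513. Rounding of the printed thresholds moves the figure only between 0.0512 and 0.0514.

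**Step 3: does any O'Brien-Fleming version give both numbers?** For each version, find the t at which the interim level is 0.0054, then solve for the final level that holds 0.05.

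| Version | t giving 0.0054 | Matching final level | Pair at t = 0.5 |
|---|---|---|---|
| Lan-DeMets, 0.025 per side | 0.558 | 0.0483 | 0.0031/0.0490 |
| Lan-DeMets form, 0.05 spent two-sided | 0.496 | 0.0478 | 0.0056/0.0478 |
| Classical | 0.506 | 0.0479 | 0.0052/0.0480 |

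None gives 0.0492. At t = 0.70, where the stated pair does hold 0.05, the classical pair is 0.0164/0.0446.

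**Step 4: exact check with the planned test.** Binomial enumeration of the uncorrected chi-square, with 41 then 82 per arm:

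| Common true rate | Error, 0.0054/0.0492 | Error, 0.0054/0.0479 |
|---|---|---|
| 50% | 0.0527 | 0.0527 |
| 60% | 0.0496 | 0.0489 |
| 70% | 0.0524 | 0.0511 |
| 80% | 0.0529 | 0.0494 |
| Mean, 50% to 90% in steps of 5 points | 0.0514 | 0.0503 |

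**Step 5: which final results change.** With 0.0054 kept, only a final p between 0.0479 and 0.0492 is affected. With AI higher and at least 50% screened in each arm, two tables lie there: 60 versus 48 screened (p = 0.0481) and 71 versus 61 (p = 0.0488). Under 60% versus 80%, all tables in the band have a total probability of 0.3%.

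**The case against.** The arithmetic and the omission are not in dispute; the weight is.

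- **Halfway is an assumption.** This stands. The √2 ratio makes it likely but does not prove it, and from about 70% information the stated pair holds 0.05. A later look would still leave E2 naming a rule that its numbers do not follow.
- **The excess is tiny.** This also stands. Whatever the look time, the pair cannot exceed 1 − (1 − 0.0054)(1 − 0.0492) = 0.0543 under the normal approximation. The excess of 0.0013 at a halfway look is similar in size to the discreteness of the chi-square test, and at the planned 60% rate the exact error is 0.0496. The replacement pair does not hold 0.05 at every true rate either (0.0527 at 50%).
- **The DSMB may choose not to stop.** If a crossing is not acted on and the claim rests on the final test alone, the error is 0.0492. But E2 also says that the trial will stop on a crossing, so a crossing can support the claim and has to be counted.

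These points limit the size of the problem. They do not supply the missing look time or make the two thresholds agree.

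**Conclusion.** The concern holds. E2 omits the look time and the version of the rule; that part needs no assumption. If the look is halfway, as the thresholds suggest, the stated pair has a joint two-sided error of 0.0513 rather than 0.05. This rests on the normal approximation and on counting every interim crossing as a rejection. No look time yields both thresholds under the three O'Brien-Fleming versions computed. The numerical effect is small and unlikely to change the trial's conclusion. The point should still be fixed, because these are the decision thresholds for the primary outcome and the correction costs almost nothing.

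**What to change.** In E2, state three things before anyone sees comparative data:

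1. **The look time**, as an information fraction counted in participants whose outcome is determined in both arms. In the AI arm a normal screen settles the outcome at the visit, while controls have up to 6 months (C1, D2), so halfway by enrolment and halfway by known outcomes are different looks.
2. **The O'Brien-Fleming version.**
3. **A pair of levels that holds 0.05 for it** under the normal approximation. If a spending function is used and the actual fraction differs from plan, recompute the levels from the actual fraction.

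Options at a halfway look, with exact operating characteristics for 60% versus 80% and 82 per arm:

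| Pair | Basis | Power | Chance of crossing at the interim |
|---|---|---|---|
| 0.0054/0.0492 | As written | 80.9% | 21.6% |
| 0.0054/0.0479 | Smallest change | 80.7% | 21.6% |
| 0.0052/0.0480 | Classical O'Brien-Fleming | 80.6% | 20.4% |
| 0.0031/0.0490 | Lan-DeMets, 0.025 per side | 80.8% | 16.1% |

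If 0.0054 is kept and the look is not halfway, take the final level from the Step 2 table. The cost is wording in E2 and at most 0.3 percentage points of power (80.9% to 80.6%), with no added participants. The Lan-DeMets pair makes early stopping less likely.

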In the intervention arm, or autonomous AI arm, participants will undergo point of care diabetic eye exams using autonomous AI in the pediatric diabetes clinic, and will receive immediate results from autonomous AI. If the screen is normal, they have completed their screening. If the AI screen is abnormal, they will then be referred to ECP for further examination and will receive a scripted educational intervention. If the images are insufficient for interpretation, they will be referred to ECP for further examination and will receive a scripted educational intervention.

Followup: After randomization in the study, participants will have 6 months to complete the diabetic eye exam (in the control arm) or follow-up eye exam (in the intervention arm if AI abnormal). If the exam is not complete by 6 months, or the participant cannot be reached to determine completion of the exam, it will be considered not done.

C2 Subject Selection and Withdrawal

2.a Inclusion Criteria

- T1D: 11 years of age or older or in puberty, with diabetes for at least 3 years (ADA guidelines)⁶
- T2D: at diagnosis and thereafter (ADA guidelines)
- No known diabetic retinopathy
- No diabetic retinopathy exam within the last 6 months

2.a Exclusion Criteria

- Known diabetic eye disease

2.b Subject Recruitment Plans and Consent Process

Individual(s) responsible for approaching participant(s): Research coordinators

Where and when recruitment will take place:

Participants will be recruited, screened for eligibility, and consented in a private clinic/room to ensure privacy.

Consent process:

Participants will read through the consent form with the research coordinator, have time to review it and ask questions about the study and study procedures.

2.c Randomization Method and Blinding

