To prevent selection bias and ensure sample size balance between the groups and sites, a stratified randomization (by site) scheme was developed with participants randomized in permuted block schedules of 4 and 6. Within each block, participants are randomized with a 1:1 allocation ratio to the control group and intervention group. This randomization sequence was created by a statistician unaffiliated with the study to ensure masking, and then another unaffiliated statistician entered the randomization scheme into REDCAP's randomization software.⁷ After consent, the research coordinator will enter the participant location, and the randomization allocation is generated. All parties are masked to the allocation until the participant is randomized, and then all parties are unmasked.

2.d Risks and Benefits

This study involves no medical risks to the participants because of the non-invasive nature and lack of use of dilating eye drops for fundus photography. The only potential risk is related to privacy issues, should data with identifiers become non-secure.

Confidentiality: There is the risk that psychological, emotional, financial, social, and legal risks might result if confidentiality cannot be maintained in this study. All study team members are HIPPA trained and will take every step to respect participants' privacy and

protect their confidentiality throughout the study. We share the information gathered in the study only with the people who need to know this information. All information gathered during this study will be kept in a secure HIPAA compliant database, REDCap.

Benefit: Undergoing diabetic eye exam screening can lead to possible detection of diabetic retinopathy and allow for appropriate timely management.

2.e Early Withdrawal of Subjects

Participants may withdraw from the study at any time by notifying the study team.

2.f When and How to Withdraw Subjects

The participant may choose to withdraw from the study. The study visit is a one-time study visit, so once the participant is enrolled, if they choose to withdraw, it will not affect study procedures. It will also not impact the course of the participant's clinical care.

2.g Data Collection and Follow-up for Withdrawn Subjects

Data collected from subjects will remain in the dataset as this is an intent to treat analysis, but no follow-up will be conducted on withdrawn subjects.

D Study Procedures

D1 Screening for Eligibility

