The secondary outcome is follow-up at ECP in each arm, comparing proportion of participants who arrive at ECP for DR screening in the control arm, to the proportion of participants in the AI arm who have an abnormal AI screening, are referred to ECP for follow-up, and arrive at ECP. This will be analyzed using a Pearson's chi-square test and logistic regression (adjusting for covariates).

E3. Statistical Methods

Statistical analyses will be performed using Stata 15.1 (Statacorp, College Station, TX). The primary and secondary outcomes will be further analyzed (in addition to above) using multivariate logistic regression analyses in order to examine the relationship between demographic characteristics and the outcomes. Additionally, multivariable logistic regression analyses will assess the odds of having a previous diabetic eye exam, adjusting for known covariates associated with diabetic eye disease. This will be an intent to treat analysis; all participants will be analyzed.

E4. Missing Outcome Data

Dataset will be assessed for missing-ness and noted in results.

E5. Unblinding Procedures

Not applicable

F. Data Handling and Record Keeping

F1. Confidentiality and Security

All data for this study will be recorded and stored in REDcap through Johns Hopkins Medicine.

F2. Records Retention

Informed consent documents will be securely stored in a locked file cabinet within a locked office. Informed consents will also be scanned into the participant's electronic medical record. Eye exam results from the AI camera will be uploaded into the Media section of the participant's electronic medical record in Epic.

G. Study Administration

G1. Organization and Participating Centers

Johns Hopkins Pediatric Diabetes Center
Mount Washington Pediatric Hospital Diabetes Center

G2. Funding Source

Funding for this study is provided by the National Eye Institute of the National Institutes of Health under Award Number R01EY033233 (PI: [name]), and the Diabetes Research Connection (PI: [name]).

G3. Subject Stipends or Payments

Participants received a \$25.00 gift card, and a parking pass at the study visit.

E References

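### Randomisation is stratified by site, but the primary chi-square pools the sites and no analysis names site: a minor alignment point, not a validity error

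*Combined protocol and SAP*

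**What the plan says.** - **Randomisation (section 2.c).** "To prevent selection bias and ensure sample size balance between the groups and sites, a stratified randomization (by site) scheme was developed". Permuted blocks of 4 and 6 are used within site. The stated reasons are selection bias and balance; precision is not mentioned.
- **Sites (section G1).** There are two centres, the second being "Mount Washington Pediatric Hospital Diabetes Center".
- **Primary analysis (section E3, primary outcome).** A Pearson "chi-square test (primary outcome) and logistic regression (adjusting for covariates"). No stratification is stated.
- **Secondary outcome (section E3, secondary outcomes).** "This will be analyzed using a Pearson's chi-square test and logistic regression (adjusting for covariates"). The covariates are again not listed.
- **Further models (section E3, Statistical Methods).** These refer to demographic characteristics and to known correlates of diabetic eye disease. Site is not mentioned.
- **Interim (section E2).** "One interim efficiency analysis for efficacy is planned", with a final threshold of p < 0.0492.
- **Masking (section 2.c).** "All parties are masked to the allocation until the participant is randomized, and then all parties are unmasked".

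**The concern.** The trial blocks on site and then tests its primary outcome as if site did not exist. Site may be among the unlisted covariates of the logistic models, but the primary test does not use it. When arms are balanced within site and sites have different screening rates, a pooled test carries the between-site variation in its variance. It then becomes conservative and can lose some power. At stake are a little precision and the agreement between the design and the analysis. Bias and the adequacy of the sample size are not in question.

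**Working it through.** **Inputs from the documents.** Control rate 60%; difference 20 points, so 80% with AI; two-sided alpha 0.05; power 80%; 82 per arm (section E1). Final threshold 0.0492 (section E2). 1:1 allocation (section C1). Two sites (section G1).

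**Assumptions, because the documents are silent.** Enrolment split per arm of 41:41 or 70:12. Between-site gap of 0 to 20 points. Site rates are centred so that the overall rates stay at 60% and 80%.

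**1. The plan's own figure.** Using the pooled-variance formula without continuity correction:

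n = [1.960·√(2·0.7·0.3) + 0.842·√(0.6·0.4 + 0.8·0.2)]² / 0.20² = 81.2, rounded up to 82 per arm and 164 in total.

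This matches section E1. At 0.0492 the answer is still 82 per arm. The approximate power of 82 per arm is 80.4% at 0.05 and 80.2% at 0.0492.

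**2. Why the two tests differ.** Suppose arms are equal within each site, with N in total, N_s at site s, and m and m_s screened. Both statistics then have the same numerator, the squared difference between the number screened with AI and its expectation. Only the variances differ:

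- pooled: m(N − m) / (4N)
- CMH: Σ m_s(N_s − m_s) / (4(N_s − 1))

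The pooled test works with p(1 − p) at the overall rate, 0.70 × 0.30 = 0.210. CMH uses the within-site average. At 41:41 with a 20-point gap:

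- both arms shifted (site rates 80% and 60%): (0.160 + 0.240)/2 = 0.200, which is 4.8% smaller
- control arm only (site rates 75% and 65%): (0.1875 + 0.2275)/2 = 0.2075, which is 1.2% smaller

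The N_s − 1 divisor works against this reduction, so CMH loses slightly when the sites are alike.

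**3. Exact power at 0.0492.** All binomial outcomes in the four site-by-arm cells were enumerated, with no continuity correction.

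| Split per arm | Pattern | Gap (points) | Chi-square | CMH | Change (points) |
|---|---|---|---|---|---|
| 41:41 | none | 0 | 80.74% | 80.60% | -0.15 |
| 70:12 | none | 0 | 80.74% | 80.62% | -0.12 |
| 41:41 | control arm only | 10 | 80.81% | 80.73% | -0.08 |
| 41:41 | control arm only | 20 | 81.01% | 81.15% | +0.13 |
| 41:41 | both arms | 10 | 80.89% | 81.07% | +0.18 |
| 41:41 | both arms | 20 | 81.35% | 82.54% | +1.19 |

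Changes are taken before rounding. At 70:12 with a 20-point gap, the change is -0.01 to +0.02 points (control arm only) or +0.44 to +0.52 points (both arms), depending on which site has the higher rate.

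CMH first gains power at these gaps:

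- control arm only: about 15 points (41:41) or 19 to 21 points (70:12)
- both arms: about 7 points (41:41) or 9 to 10 points (70:12)

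**4. Which pattern is more plausible.** In the AI arm, "participants will undergo point of care diabetic eye exams using autonomous AI in the pediatric diabetes clinic" (section C1), and "Randomization and study visit occur at the same time so there is little risk of attrition" (section E1). AI completion is therefore largely settled on the day. A site difference would act mainly on the control arm, where participants must arrange an outside examination.

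**5. Exact type I error of the pooled chi-square, nominal 0.0492.**

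- Sites alike: 0.0475 to 0.0508 over common rates of 50% to 85%.
- 20-point gap at 41:41: 0.0429 at a mean rate of 60% and 0.0446 at 70%. CMH gives 0.0478 and 0.0491.

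**6. Cross-check by simulation.** This used 20,000 trials per scenario, blocks of 4 and 6 within site, a common odds ratio, and site shares of 50/50, 70/30 and 85/15. For gaps of 0 to 20 points, power was 80.4% to 81.3% for the chi-square and 80.5% to 82.2% for CMH. Only an extreme 40-point gap made a clear difference: the chi-square's type I error fell to 3.1% to 3.9%, and CMH gained 2.6 to 3.4 points of power.

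**The case against.** The strongest reply is that nothing here is wrong. The chi-square is valid, the sample size holds, and the stated reason for stratifying is served whether or not the test uses site. In the control-arm-only pattern, CMH loses power until the gap reaches about 15 points, and gains at most 0.13 points at gaps up to 20. The one rate contrast in section E1, 46% of non-white against 85% of white youth with a prior examination, suggests that such gaps need very different case mix. On that contrast alone, a 15-point gap requires the sites' shares of white youth to differ by about 38 points (15/39). Against so small a gain stands a change to the primary test of a pre-registered trial in which everyone is unmasked after allocation. The protocol is also labelled final, and section G3 describes participant payment in the past tense, so it may be too late. Finally, site may already be among the unlisted covariates.

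Most of this stands, and it is why the point is minor. It limits when the primary test should be changed, but it does not remove the mismatch. The chi-square is the designated primary test, and it ignores the only factor that the randomisation is known to use. A covariate list that is never given does not settle whether the adjusted models include site. The timing objection is met by making the change of primary test conditional on no outcome data having been analysed.

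**Conclusion.** The point holds and is minor, with high confidence. Site stratifies the randomisation, the primary test pools the sites, and no analysis names site. The plan remains valid: 164 participants give about 80% power, and the type I error is close to 0.0492 when the sites are alike and below it when they differ.

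For gaps up to 20 points, a site-stratified test changes power by between -0.15 and +1.19 points. The upper end requires the same 20-point gap in both arms and equal enrolment. These sizes rest on assumed site gaps and splits. The trial's conclusion is unlikely to depend on the choice: at the pilot's 95% AI rate both tests exceed 99.9% power. The benefit is an analysis that follows the randomisation, with modest protection of precision if both arms vary by site.

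**What to change.** **If no outcome data have been analysed, including at the interim:**

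- make the primary test a CMH test stratified by site, and use it at both the interim and the final look;
- report a site-stratified Mantel-Haenszel risk difference with its confidence interval, as the estimate that accompanies that test;
- name site as a covariate in the logistic models for the primary and secondary outcomes;
- keep the unstratified chi-square as a supporting analysis.

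**If outcome data have been seen:** keep the chi-square as primary, add the site-stratified analysis as a sensitivity analysis, and name site in the logistic models.

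**Cost.** No new data are needed, because site is entered at randomisation, and the sample size does not change. If the sites turn out alike, up to about 0.15 points of power is lost. The first option also needs a documented change to the primary test of a pre-registered, unmasked trial, so it must come before any look at outcomes.

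### The primary chi-square test ignores prior eye-exam status, a baseline predictor the trial will have; stratifying on it would bring a modest, nearly free gain in efficiency

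*Combined protocol and SAP*

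**What the plan says.** E3 (Analysis Plan) assesses the primary outcome, the proportion screened, by a Pearson "chi-square test (primary outcome) and logistic regression (adjusting for covariates"). The primary label sits on the chi-square, and that sentence names no covariates.

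E3 (Statistical Methods) adds regressions relating demographic characteristics to the primary and secondary outcomes. It also states that "multivariable logistic regression analyses will assess the odds of having a previous diabetic eye exam", adjusted for covariates linked to diabetic eye disease. Prior-exam status is therefore expected to be available, but only as the dependent variable of that side model.

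E1 reports that 49% of the pilot children had a prior exam. Of youth meeting screening criteria in the preliminary data, "66% had a prior diabetic eye exam (46% non-white, 85% white youth"). Section 2.c stratifies randomisation by site only. Section 2.a excludes anyone examined in the last 6 months.

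**The concern.** Being screened in the control arm means attending an outside appointment. Whether a youth has ever attended one is the closest baseline predictor the plan mentions, and E1 itself uses exam history as background to its control-rate assumption. A crude two-by-two test makes no use of it.

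Two things follow if prior exam is prognostic. Some variance that could be explained stays in the 20-point comparison. And because prior exam is not a randomisation stratum, its split between arms of 82 is left to chance, and the crude result moves with that split in whichever direction it falls. The planned adjusted model would help only if it included prior exam, and nothing says that it will.

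**Working it through.** **1. The plan's own sample size.** Inputs from E1: "The following power calculations assume 80% power and a 2-tailed type 1 error of 0.05"; "We assume that adding the educational intervention will raise the ECP rate to 60" per cent; "we assess a 20% difference to be clinically relevant between the two" strategies. The rates are therefore 0.60 and 0.80, with mean 0.70.

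n per arm = [1.960·√(2·0.70·0.30) + 0.842·√(0.24 + 0.16)]² / 0.20² = 81.2, rounded up to 82. This reproduces the statement that the difference "results in a sample size of 164 (n=82 ECP, n=82 AI").

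E2 says that at the full sample size "the threshold for significance will be $p < 0.0492". At that level z = 1.967, and power = Φ[(0.20·√82 − 1.967·√0.42)/√0.40] = 80.2%. The crude test therefore has the power that was planned.

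**2. Size of chance imbalance.** The SD of the between-arm difference in prior-exam share is √(2π(1−π)/82), where π is that share. It is 7.8 points at π = 0.49 and 7.4 points at π = 0.66. An imbalance above 10 points in either direction has probability 18–20%. An imbalance shifts the crude risk difference by its own size times the mean of the two within-arm gradients.

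**3. Assumed associations.** The documents give none, so these are assumptions. Overall rates are held at 60% and 80%.

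| | Share with prior exam | Control: prior / none | AI: prior / none |
|---|---|---|---|
| A | 50% | 75 / 45 | 80 / 80 |
| B | 66% | 75 / 31 | 80 / 80 |
| C | 50% | 75 / 45 | 88 / 72 |
| D | 66% | 75 / 31 | 88 / 64.5 |

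**4. Variance, with A and D as examples.** The unadjusted term is 0.24 + 0.16 = 0.40. The term for a risk difference standardised over prior exam is the weighted within-stratum variance plus π(1−π)D²/2, where D is the difference between the two stratum effects.
- A: 0.5(0.1875 + 0.16) + 0.5(0.2475 + 0.16) + 0.25·0.30²/2 = 0.389, ratio 0.97.
- D: 0.66(0.1875 + 0.1056) + 0.34(0.2139 + 0.2290) + 0.2244·0.205²/2 = 0.349, ratio 0.87.

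**5. Simulated power at 0.0492** (at least 200,000 trials per cell; each cell shows crude chi-square, then Cochran-Mantel-Haenszel, CMH). The imbalance columns fix a gap of 6/82 = 7.3 points, about one SD.

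| | Average | Imbalance against AI | Imbalance favouring AI |
|---|---|---|---|
| A | 80.8, 81.3 | 77, 82 | 85, 82 |
| B | 80.6, 81.8 | 75, 83 | 87, 83 |
| C | 80.7, 82.8 | 74, 83 | 87, 83 |
| D | 80.8, 85.3 | 71, 85 | 91, 85 |

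The 7.3-point gap shifts the crude difference by 7.3·(0.30 + 0)/2 = 1.1 points in A and 7.3·(0.44 + 0.235)/2 = 2.5 points in D.

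**6. Weaker and null associations.** At an odds ratio of 2 the average change runs from −0.3 point (control arm only) to about +0.4 (both arms). At an odds ratio of 4 it is about +0.4 to +0.6 in the control arm only and +3 in both. With no association, CMH loses about 0.4 to 0.6 point. Under the null, CMH rejects in about 4.9% of trials.

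**The case against.** Several stronger readings are tempting, and the documents do not support them.

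- A reader might infer that imbalance in past attendance goes uncorrected. E3 plans a covariate-adjusted logistic model of the primary outcome and names demographics for a further regression. The gap is narrower: prior exam is not named, and the adjusted model is not the labelled primary test.
- A reader might call prior exam the baseline value of the outcome. It is not. E3 sets no time limit on a previous exam, everyone enrolled is unscreened for the last 6 months, and youth with type 2 diabetes can enter at diagnosis, before any exam was due. It is a plausible predictor only. That it is recorded for each participant is inferred from the side model; D1 confirms only the last 6 months.
- A reader might treat the fall to 71–77% power under an adverse split as an extra loss. The opposite split is equally likely and raises crude power to 85–91%. The average stays near 81%, so these swings are already part of the design power.

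The AI exam is done in clinic at the study visit, so past attendance has little obvious route to affect it. That makes rows A and B the more plausible ones, with gains of about a point. If the AI rate approached the pilot's 95%, power against 60% would be close to 100% with either test.

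All of this stands, and it limits the point to modest efficiency. It does not remove the point: an available predictor is left out of the deciding test, and using it costs very little.

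**Conclusion.** The point holds as one of efficiency and prespecification. The unadjusted chi-square is valid, its type I error is kept, and N = 164 matches it; nothing here shows an error in the primary result or a shortfall in power.

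Under the assumed associations, stratifying by prior exam adds about 0.5 to 1 power point if prior exam matters only in the control arm, and about 2 to 4.5 points if it matters in both. With a weak association the average gain is nil. The steadier benefit is that the conclusion depends far less on how past attenders happen to fall between the arms: in the scenarios above the stratified test stays at 82–85% power under a one-SD imbalance either way, while the crude test ranges from 71% to 91%.

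The size rests on associations that the documents do not give, and on prior-exam status being recorded at baseline for every participant.

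**What to change.** In E3, before any outcome comparison by arm:

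- Make the primary test a Cochran-Mantel-Haenszel test stratified by prior diabetic eye exam (yes/no), at the E2 thresholds (0.0054 at the interim look, 0.0492 at the end).
- Report the risk difference standardised over that factor as the accompanying estimate. The logistic odds ratio is on a different scale and does not replace it.
- Name prior exam and site, the randomisation stratifier, as covariates in the planned logistic model.
- Keep the crude Pearson chi-square as a sensitivity analysis.
- Confirm that prior-exam status is recorded at baseline for every participant.

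If the team prefers to leave the chi-square as primary, naming prior exam and site in the adjusted model is the minimum.

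Cost: wording and a few lines of code, with no change to N and no new visits. If prior exam predicts nothing, about 0.4 to 0.6 power point is lost. If enrolment has begun, changing the deciding test needs a protocol amendment. The documents do not settle that, though G3 describes participant payments in the past tense. Because all parties are unmasked after randomisation (section 2.c), the amendment should record that it was made without sight of outcomes by arm.
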